Statistical Analysis Plan Amendment 3**1. DOCUMENT HISTORY**

Date	Description	Protocol Version
29 OCT 2019	first version	Final: 09 JUL 2019
10 MAR 2020	Amendment 1	Amendment 1: 27 JAN 2020
29 MAY 2020	Amendment 2	Amendment 2: 19 MAY 2020
02 NOV 2020	Amendment 3	Amendment 3: 30 SEP 2020

Table below lists main changes in the SAP amendment 3 and their rationale

Section # and Name	Description of Change	Brief Rationale
7.1.2 Second analysis 7.1.3 Third analysis Section 3, table 2	Observer blind removed following 2 nd analysis	After the second analysis, the study will not be considered observer blind as the investigator brochure will be updated to include safety information presented by treatment group. This could lead to inadvertent unblinding of investigators and site staff to some subjects' treatment assignments. The subjects themselves will remain blinded throughout their participation in the study.

CONFIDENTIAL209544 (RSV MAT-004)
Statistical Analysis Plan Amendment 3**2. OBJECTIVES/ENDPOINTS****Table 1 Study objectives and endpoints**

Primary Safety objectives	Primary Safety endpoint(s)
To evaluate the safety and reactogenicity of a single IM dose of study vaccine administered to maternal subjects, from Visit 1 up to 6 weeks after delivery	Occurrence of solicited administration site and systemic events during a 7-day follow-up period after vaccination (i.e. the day of vaccination and 6 subsequent days).
	Occurrence of any hematological (complete blood count with differential and platelet count) or biochemical (alanine amino-transferase, aspartate amino-transferase, creatinine, blood urea nitrogen) laboratory abnormality at baseline (up to 15 days before vaccination) and Day 8 (Visit 2)
	Occurrence of unsolicited AEs that occur during a 30-day follow-up period after vaccination (i.e. the day of vaccination and 29 subsequent days).
	Occurrence of serious adverse events (SAEs), AEs leading to study withdrawal, and medically attended AEs (MAEs) from Visit 1 (Day 1) up to 6 weeks after delivery (Day 43 post-delivery, Visit 6).
To evaluate pregnancy outcomes and pregnancy-related AESIs after a single IM dose of study vaccine administered to maternal subjects, from Visit 1 up to 6 weeks after delivery (Visit 6).	Pregnancy outcomes from Day 1 (Visit 1) up to 6 weeks after delivery (Day 43 post-delivery, Visit 6). These include live birth with no congenital anomalies, live birth with congenital anomalies, fetal death/still birth (antepartum or intrapartum) with no congenital anomalies, fetal death/still birth (antepartum or intrapartum) with congenital anomalies, elective/therapeutic termination with no congenital anomalies and elective/therapeutic termination with congenital anomalies.
	Pregnancy-related AESIs from Day 1 (Visit 1) up to 6 weeks after delivery (Day 43 post-delivery, Visit 6). These include but are not limited to maternal death, hypertensive disorders of pregnancy (gestational hypertension, pre-eclampsia, pre-eclampsia with severe features including eclampsia), antenatal bleeding (morbidly adherent placenta, placental abruption, cesarean scar pregnancy, uterine rupture), postpartum hemorrhage, fetal growth restriction, gestational diabetes mellitus, non-reassuring fetal status, pathways to preterm birth (premature preterm rupture of membranes, preterm labor, provider-initiated preterm birth), chorioamnionitis, oligohydramnios, polyhydramnios, gestational liver disease (intrahepatic cholestasis of pregnancy, acute fatty liver of pregnancy), maternal sepsis.*
To evaluate the safety of the study vaccine, including neonatal AEs of special interest, in infants born to maternal subjects who were vaccinated with a single IM dose of study vaccine, up to 6 weeks after birth.	The occurrence of neonatal AEs of special interest (reported up to 6 weeks after birth). These include but are not limited to small for gestational age, low birth weight including very low birth weight, neonatal encephalopathy, congenital microcephaly (postnatally or prenatally diagnosed), congenital anomalies (major external structural defects, internal structural defects, functional defects), neonatal death (in a preterm live birth or in a term live birth), neonatal infections (blood stream infections, meningitis, respiratory infection), respiratory distress in the neonate, preterm birth, failure to thrive, large for gestational age, macrosomia.* Occurrence of SAEs, AEs leading to study withdrawal and MAEs from birth up to 6 weeks after birth.

CONFIDENTIAL209544 (RSV MAT-004)
Statistical Analysis Plan Amendment 3

Primary Immunogenicity objectives	Primary Immunogenicity endpoints
To evaluate the immunogenicity of a single IM dose of study vaccine in maternal subjects at Day 31 and at Delivery.	RSVPreF3 IgG-specific antibody concentration, and Neutralizing antibody titers against RSV-A Measured on blood samples collected from vaccinated maternal subjects at Day 1 before vaccination (Visit 1), Day 31 (Visit 3), and at Delivery (Visit 5).
To evaluate RSV-specific antibody levels in infants born to maternal subjects who were vaccinated with a single IM dose of study vaccine at birth j	RSVPreF3 IgG-specific antibody concentration, and Neutralizing antibody titers against RSV-A. Measured on the cord blood sample collected at delivery, or on a blood sample collected from the infant within 3 days after birth (if no cord blood sample can be obtained).
To evaluate the transfer of RSV-specific antibodies from maternal subjects vaccinated with a single IM dose of study vaccine to their infants at the time of delivery.	The ratio between cord blood* and maternal RSVPreF3 IgG-specific antibody concentrations *or an infant blood sample collected within 3 days after birth (if no cord blood sample can be obtained).
Secondary Safety objectives	Secondary Safety endpoints
To evaluate the safety of a single IM dose of study vaccine in maternal subjects, up to 6 months after delivery	From Day 1 (Visit 1) through 6 months after delivery (Visit 8), occurrences of SAEs, MAEs, and AEs leading to study withdrawal.
To evaluate the safety of the vaccine in infants born to maternal subjects who were vaccinated with a single IM dose of study vaccine, up to 1 year of age	From birth through 6 months (Visit 4-NB) after birth, occurrences of SAEs, AEs leading to study withdrawal, and MAEs From birth through 1 year (Visit 5-NB) after birth, occurrences of SAEs, AEs leading to study withdrawal, and MAEs.
To estimate the incidence of RSV-associated, medically attended RTIs (MA-RTIs) in maternal subjects vaccinated with a single IM dose of study vaccine, from vaccination up to 6 months post-delivery (Visit 8).	Occurrence of RSV-associated MA-RTIs (RSV-MA-RTIs) up to 6 months post-delivery (Visit 8)
To estimate the incidence of RSV-associated lower respiratory tract illness (LRTI), severe LRTI and very severe LRTI and RSV-associated hospitalization in infants born to maternal subjects who were vaccinated with a single IM dose of study vaccine, from birth up to 6 months of age.	From birth to 6 months (Visit 4-NB), occurrences of RSV-associated LRTI(s), Severe LRTI(s), very severe LRTIs and RSV-associated hospitalizations (according to the case definitions).

CONFIDENTIAL209544 (RSV MAT-004)
Statistical Analysis Plan Amendment 3

Secondary immunogenicity objectives	Secondary Immunogenicity endpoints
To evaluate the immunogenicity of a single IM dose of study vaccine in maternal subjects in terms of RSVPreF3 IgG-specific antibody concentrations and neutralizing antibodies against RSV-A at Day 43 after Delivery (Visit 6).	RSVPreF3 IgG-specific antibody concentration Neutralizing antibody titers against RSV-A Measured on the blood sample collected at Day 43 post- delivery (Visit 6).
To evaluate the immunogenicity of a single IM dose of study vaccine in maternal subjects in terms of RSV-B neutralizing antibodies at Day 1 before vaccination (Visit 1), Day 31 (Visit 3), at Delivery (Visit 5) and at Day 43 post-delivery (Visit 6).	Neutralizing antibody titers against RSV-B Measured on blood samples collected from vaccinated maternal subjects at Day 1 before vaccination (Visit 1), Day 31 (Visit 3), at Delivery (Visit 5) and at Day 43 post-delivery (Visit 6).
To evaluate RSV-specific antibodies in infants born to maternal subjects who were vaccinated with a single IM dose of study vaccine, up to 6 months after birth.	RSVPreF3 IgG-specific antibody concentration Neutralising antibody titres against RSV-A Neutralising antibody titres against RSV-B For neutralizing antibody titers against RSV-B only: measured on the cord blood sample collected at delivery, or on a blood sample collected from the infant within 3 days after birth (if no cord blood sample can be obtained). (Note: RSV-A neutralizing antibody at birth is a primary immunogenicity objective). For all 3 RSV-specific antibody assessments: measured in a subcohort of infants at Day 43 after birth (sub-cohort V2-NB), in a subcohort of infants at Day 121 (sub-cohort V3-NB) after birth and in a subcohort of infants at D181 after birth (sub-cohort V4-NB). Each infant will be randomly assigned to 1 of these 3 cohorts at the time of maternal randomization to treatment study intervention.
Tertiary objectives: To further evaluate the humoral response to the RSV maternal vaccine, which may include RSVpreF3 specific IgG subclasses, antibodies competing for binding to specific RSVpreF3 epitopes, and other exploratory endpoints. To evaluate the presence of other respiratory viruses in nasal swabs collected from maternal subjects and their infants (via an Allplex Respiratory Viruses Panel or alternative, performed for RSV A/B-positive samples and if deemed necessary for RSV A/B-negative samples.)	

*Maternal and neonatal AESI and pregnancy outcomes should be recorded in the eCRF along with GAIA assessment and level of diagnostic certainty when applicable. Of note, some events of interest fall under a single category but have multiple subcategories. For example, hypertensive disorders of pregnancy is an event with three subcategories that include: 1) gestational hypertension; 2) pre-eclampsia; and 3) pre-eclampsia with severe features (including eclampsia). For each event, the investigator should identify the event and select the applicable sub-category."

[figure not shown]
CONFIDENTIAL

209544 (RSV MAT-004)
Statistical Analysis Plan Amendment 3

3. STUDY DESIGN

Figure 1 and Figure 2 provide overviews of the study design for maternal and infant subjects, respectively.

Figure 1 Overall design – maternal subjects

H/B= hematology/biochemistry, Hct- hematocrit, I= humoral immune response

If Screening blood sample collected \leq 15 days before Visit 1, hematology/biochemistry not required at Visit 1

[figure not shown]
Subjects will be vaccinated year-round and will not be limited to seasonal enrolment

*Pregnancy-related AESIs identified after Day 43 will continue to be reported as such.

CONFIDENTIAL

209544 (RSV MAT-004)
Statistical Analysis Plan Amendment 3

Figure 2 Overall design– infant subjects

NB = Newborn; I=humoral immune response: infants will be randomized 1:1:1 to one of the 3 subcohorts shown.

*Blood sample to be collected within 3 days after birth **ONLY** if a cord blood sample is not collected

**Neonatal AESIs identified after Day 43 (e.g., congenital anomalies) will continue to be reported as such.

***Infant subjects' parent(s)/LAR(s) will be contacted at least monthly to ensure RTI eDiary compliance.

Safety and disease surveillance data collected *after* Visit 4-NB will be reported in the database *in Epoch 003*.

- Study Type: self-contained.
- Experimental design: Phase II, observer-blind, randomised, placebo controlled, multi-centric, multi-country study with 3 parallel groups.
- Study Duration: Approximately 9 months (including the screening visit) for participating pregnant women; approximately 1 year after birth for participating infants.
- Control: Placebo.
- Epochs 001, 002 and 003 begin and end as described in [Table 2](#).
- Blinding is as described in [Table 2](#).
- Randomized intervention allocation: **Up to** 300 eligible pregnant women will be randomly assigned to 3 study (intervention) groups in a 1:1:1 ratio and at the same time, their (as yet unborn) infants will be randomly assigned to 3 blood sampling subcohorts (also in a 1:1:1 ratio) using an automated internet based system (SBIR). The system's randomisation algorithm will use a minimisation procedure accounting for maternal age at the time of vaccination (≥ 18 and < 35 years of age or ≥ 35 years of age), gestational age at the time of vaccination ($28^{0/7}$ - $31^{0/7}$; $31^{1/7}$ - $33^{6/7}$) and center. Minimisation factors will have equal weight in the minimisation algorithm.
- Study (intervention) groups are described in [Table 2](#)

CONFIDENTIAL

209544 (RSV MAT-004)
Statistical Analysis Plan Amendment 3**Table 2 Study groups, subcohorts, interventions, epochs and blinding foreseen in the study (Amended 02-NOV-2020)**

Study groups (Maternal subjects, allocated 1:1:1)	Approximate Number of maternal subjects	Age of maternal subject at enrolment (Min/Max)	Intervention name	Blood sample subcohorts (infant subjects, allocated 1:1:1 within each maternal study group)	Approximate Number of infant subjects	Study groups for randomization (Allocation 1:1:1:1:1:1:1:1)	Epochs (Blinding)		
							Epoch 001 Maternal subjects Only (Screening)	Epoch 002 Maternal subjects V1-V8 Infant subjects V1-NB – V4NB (observer-blind)*	Epoch 003 Infant subjects only Contact 1-NB – V5- NB (single-blind)
RSV MAT 60	Up to 100	18 – 40 years	RSVPreF3_60	BS1_60	Up to 33	RSVMAT60_BS1	•	•	•
				BS2_60	Up to 33	RSVMAT60_BS2		•	
				BS3_60	Up to 33	RSVMAT60_BS3		•	
RSV MAT 120	Up to 100	18 – 40 years	RSVPreF3_120	BS1_120	Up to 33	RSVMAT120_BS1	•	•	•
				BS2_120	Up to 33	RSVMAT120_BS2		•	
				BS3_120	Up to 33	RSVMAT120_BS3		•	
Control	Up to 100	18 – 40 years	Control	BS1_C	Up to 33	Control_BS1	•	•	•
				BS2_C	Up to 33	Control_BS2		•	
				BS3_C	Up to 33	Control_BS3		•	

M=maternal subject; I=infant; Control = Placebo; Blood sampling subcohorts are abbreviated "BS1," "BS2," "BS3" and correspond to visits 2-NB (Day 43), 3-NB (Day 121) and 4-NB (Day 181), respectively.

* After the second analysis, the study will not be considered observer blind as the investigator brochure will be updated to include safety information presented by treatment group. This could lead to inadvertent unblinding of investigators and site staff to some subjects' treatment assignments. The subjects themselves will remain blinded throughout their participation in the study.

- Data collection: standardized Electronic Case Report Form (eCRF). Electronic diaries (e-diaries) for solicited event data, and notifications regarding occurrence of unsolicited events (including medically attended events and SAEs), and symptoms of respiratory tract illnesses in infant subjects.
- Safety monitoring: This study will be monitored by a blinded safety review team (SRT) composed of GSK RSV team members, and by an unblinded, independent data monitoring committee (IDMC) external to GSK. The analyses for IDMC safety evaluations will be described in a separate SAP for IDMC.

CONFIDENTIAL209544 (RSV MAT-004)
Statistical Analysis Plan Amendment 3**4. ANALYSIS SETS****4.1. Definition**

For purposes of analysis, the following analysis sets are defined:

4.1.1. Maternal Subjects

	Description
Analysis Set	Maternal subjects
Enrolled	All maternal subjects who completed the informed consent process and signed the informed consent form.
Exposed	All maternal subjects who received at least 1 dose of the study intervention. The allocation in a group is done in function of the administered intervention.
Full Analysis	All maternal subjects in the Exposed set who have post-vaccination immunogenicity data.
Per Protocol	All maternal subjects who received at least 1 dose of the study intervention to which they were randomised and have post-vaccination data (Full Analysis Set) minus subjects with protocol deviations that lead to exclusion.
Unsolicited Safety	All maternal subjects who received at least 1 dose of the study intervention (Exposed Set) that report unsolicited AEs/report not having unsolicited AEs
Solicited Safety	All maternal subjects in the Exposed Set who have solicited safety data

4.1.2. Infant subjects

	Description
Analysis Set	
Exposed	Infants live-born to exposed maternal subjects, whose parents/LARs completed the informed consent process and signed the informed consent form
Full Analysis	All infant subjects in the Exposed set who have post-delivery/birth immunogenicity data.
Per Protocol	All infant subjects in the Full Analysis set minus those who (a) were born less than 4 weeks post- maternal subject vaccination and/ or (b) have protocol deviations that lead to exclusion.
Unsolicited Safety	All infants in the exposed set for whom unsolicited AEs /not having unsolicited AEs are reported

4.1.3. Randomized Set

Randomized set will include all maternal subjects who are randomized and all of their randomized infants. The allocation in a group is done as function of the randomized intervention. Please note this set was not included in the protocol, but will be used later in one summary analysis, so it is added here for clarification.

4.1.4. Full Analysis Set

Full analysis set will be defined by time point. For infants, it will include all of the infants in the Exposed Set who have immunogenicity data at the corresponding time point after birth.

CONFIDENTIAL209544 (RSV MAT-004)
Statistical Analysis Plan Amendment 3**4.2. Criteria for eliminating data from Analysis Sets**

Elimination codes are used to identify subjects to be eliminated from analysis. Detail is provided below for each set.

4.2.1. Elimination from Exposed Set (ES)

Maternal subjects: Code 1030 (Study vaccine not administered at all), 800 (Fraudulent data) and code 900 (invalid informed consent) will be used for identifying maternal subjects eliminated from ES

Infants: Code 1030 (Study vaccine not administered at all, carry forward elimination from mother to infant), 800 (Fraudulent data), code 900 (invalid informed consent) and code 901 (invalid informed consent due to mother) will be used for identifying infants eliminated from ES

4.2.2. Elimination from Full Analysis Set (FAS)**4.2.2.1. Excluded subjects from FAS of maternal subjects**

A maternal subject will be excluded from the FAS analysis under the following conditions

Table 3 Elimination code and condition for maternal subjects

Code	Condition under which the code is used	Visit (timepoints) where the code is applicable	Applicable for analysis set/endpoint
800	Fraudulent data	All	All
900	Invalid informed consent	All	All
1030	Study vaccine not administered at all	All	Safety, immunogenicity
2100.Vx	Serological results not available post-vaccination	Visit 3/Day 31, Visit 5/Delivery Visit 6/Day 43 Post-Delivery	Immunogenicity

Vx indicates subjects whose immunogenicity data will be eliminated from a specific visit.

CONFIDENTIAL209544 (RSV MAT-004)
Statistical Analysis Plan Amendment 3**4.2.2.2. Excluded subjects from FAS of infant subjects**

An infant subject will be excluded from the FAS analysis under the following conditions

Table 4 Elimination code and condition for infant subjects

Code	Condition under which the code is used	Visit (timepoints) where the code is applicable	Applicable for analysis set/endpoint
800	Fraudulent data	All	All
900	Invalid informed consent	All	All
901#	Invalid informed consent - mother	All	All
1030#	Study vaccine not administered at all - mother	All	Safety, immunogenicity
2100.Vx	Serological results not available	Visit 1-NB/Birth* Visit 2-NB/Day 43 post-birth Visit3-NB/Day 121 post-birth Visit4-NB/Day 181 post-birth	Immunogenicity

#Carry forward elimination from mother to infant

Vx indicates subjects whose immunogenicity data will be eliminated from a specific visit.

*cord blood sample or blood sample collected within 3 days after birth if cord blood sample is not collected

CONFIDENTIAL209544 (RSV MAT-004)
Statistical Analysis Plan Amendment 3**4.2.3. Elimination from Per-protocol analysis Set (PPS)****4.2.3.1. Excluded subjects from Per-protocol analysis set of maternal subjects**

A maternal subject will be excluded from the PPS analysis under the following conditions

Table 5 Elimination code and condition for maternal subjects

Code	Condition under which the code is used	Visit (timepoints) where the code is applicable	Applicable for analysis set/endpoint
800	Fraudulent data	All	All
900	Invalid informed consent	All	All
1030	Study vaccine not administered at all	All	Safety, immunogenicity
1040.Vx+*	Administration of concomitant vaccine(s) forbidden in the protocol	Visit 3/Day 31, Visit 5/Delivery Visit 6/Day 43 Post-Delivery	Immunogenicity
1050	Randomisation failure	All	Immunogenicity
1060	Randomisation code was broken	All	Immunogenicity
1070**	Subjects got vaccinated with the correct vaccine but containing an incorrect volume	All	Immunogenicity
1070**	Vaccination not according to protocol (site of injection, route of administration, wrong replacement of study treatment administered)	All	Immunogenicity
1070**	Study treatment not prepared as per protocol (e.g. reconstitution)	All	Immunogenicity
1070**	Other deviations related to wrong study treatment/administration/dose	All	Immunogenicity
1070**	Study treatment administered while contraindication	All	Immunogenicity
1080	Vaccine temperature deviation	All	Immunogenicity
1090	Expired vaccine administered	All	Immunogenicity
2010	Protocol violation (inclusion/exclusion criteria) DOB – VAC – 18-40 years Gestational age at vaccination - 28 0/7 – 33 6/7	All	Immunogenicity
2040.Vx+*	Administration of any medication forbidden by the protocol	Visit 3/Day 31, Visit 5/Delivery Visit 6/Day 43 Post-Delivery	Immunogenicity
2040.Vx+*	Device, excluded by the protocol, was administered	Visit 3/Day 31, Visit 5/Delivery Visit 6/Day 43 Post-Delivery	Immunogenicity
2050.Vx+*	Intercurrent medical conditions which are exclusionary as per protocol	Visit 3/Day 31, Visit 5/Delivery Visit 6/Day 43 Post-Delivery	Immunogenicity

CONFIDENTIAL209544 (RSV MAT-004)
Statistical Analysis Plan Amendment 3

Code	Condition under which the code is used	Visit (timepoints) where the code is applicable	Applicable for analysis set/endpoint
2060.Vx+*	Concomitant infection related to the vaccine which may influence immune response	Visit 3/Day 31, Visit 5/Delivery Visit 6/Day 43 Post-Delivery	Immunogenicity
2070.Vx+*	Concomitant infection not related to the vaccine but may influence immune response	Visit 3/Day 31, Visit 5/Delivery Visit 6/Day 43 Post-Delivery	Immunogenicity
2090.Vx	Subjects did not comply with blood sample schedule: 
 For PPS at Day 31, check the interval from vaccination to day 31 BS = 20 –45 days; For PPS at Delivery, check the interval from delivery to delivery BS = (-1) – (+3) days; For PPS at Day 43 post-delivery, check the interval from delivery to day 43 post-delivery BS = 40 – 60 days 	Visit 3/Day 31, Visit 5/Delivery Visit 6/Day 43 Post-Delivery	Immunogenicity
2100.Vx	Serological results not available post-vaccination	Visit 3/Day 31, Visit 5/Delivery Visit 6/Day 43 Post-Delivery	Immunogenicity
2120.Vx	Obvious incoherence or abnormality or error in data	Visit 3/Day 31, Visit 5/Delivery Visit 6/Day 43 Post-Delivery	Immunogenicity
2130.Vx	Testing performed on samples not aligned with ICF	Visit 3/Day 31, Visit 5/Delivery Visit 6/Day 43 Post-Delivery	Immunogenicity

*Attribution of these elimination codes to subject need CRDL review of individual listing

** Attribution of code 1070 to a subject requires CRDL confirmation

Vx+ indicates subjects whose immunogenicity data will be eliminated from a specific visit onwards; Vx indicates subjects whose immunogenicity data will be eliminated from a specific visit.

DOB-Date of Birth, VAC-Vaccination, BS- Blood Sample

CONFIDENTIAL209544 (RSV MAT-004)
Statistical Analysis Plan Amendment 3**4.2.3.2. Excluded subjects from Per-protocol analysis set of infant subjects**

An infant subject will be excluded from the PPS analysis under the following conditions

Table 6 Elimination code and condition for infant subjects

Code	Condition under which the code is used	Visit (timepoints) where the code is applicable	Applicable for analysis set/endpoint
800	Fraudulent data	All	All
900	Invalid informed consent - infant	All	All
901#	Invalid informed consent - mother	All	All
1030#	Study vaccine not administered at all	All	Safety, immunogenicity
1040.Vx+*	Administration of concomitant vaccine(s) forbidden in the protocol - infant	Visit 2-NB/Day 43 post-birth Visit3-NB/Day 121 post-birth Visit4-NB/Day 181 post-birth	Immunogenicity
1041#*	Maternal administration of concomitant vaccine(s) forbidden in the protocol up to Delivery	All	Immunogenicity
1050#	Maternal randomisation failure	All	Immunogenicity
1060#	Maternal randomisation code was broken	All	Immunogenicity
1070#	Subjects got vaccinated with the correct vaccine but containing an incorrect volume	All	Immunogenicity
1070#	Vaccination not according to protocol (site of injection, route of administration, wrong replacement of study treatment administered)	All	Immunogenicity
1070#	Study treatment not prepared as per protocol (e.g. reconstitution)	All	Immunogenicity
1070#	Other deviations related to wrong study treatment/administration/dose	All	Immunogenicity
1070#	Study treatment administered while contraindicated	All	Immunogenicity
1080#	Vaccine temperature deviation	All	Immunogenicity
1090#	Expired vaccine administered	All	Immunogenicity
2010	Protocol violation (inclusion/exclusion criteria) - infant	All	Immunogenicity
2011#	Protocol violation (inclusion/exclusion criteria) - mother	All	Immunogenicity
2040.Vx+*	Administration of any medication forbidden by the protocol - infant	Visit 2-NB/Day 43 post-birth Visit3-NB/Day 121 post-birth Visit4-NB/Day 181 post-birth	Immunogenicity
2040.Vx+*	Device, excluded by the protocol, was administered - infant	Visit 2-NB/Day 43 post-birth Visit3-NB/Day 121 post-birth Visit4-NB/Day 181 post-birth	Immunogenicity

CONFIDENTIAL209544 (RSV MAT-004)
Statistical Analysis Plan Amendment 3

Code	Condition under which the code is used	Visit (timepoints) where the code is applicable	Applicable for analysis set/endpoint
2041#*	Maternal administration of any medication forbidden by the protocol up to Delivery	All	Immunogenicity
2041#*	Device, excluded by the protocol, was administered by mother up to Delivery	All	Immunogenicity
2050.Vx+*	Intercurrent medical conditions which are exclusionary as per protocol - infant	Visit 2-NB/Day 43 post-birth Visit3-NB/Day 121 post-birth Visit4-NB/Day 181 post-birth	Immunogenicity
2060.Vx+*	Concomitant infection related to the vaccine which may influence immune response - infant	Visit 2-NB/Day 43 post-birth Visit3-NB/Day 121 post-birth Visit4-NB/Day 181 post-birth	Immunogenicity
2070.Vx+*	Concomitant infection not related to the vaccine but may influence immune response - infant	Visit 2-NB/Day 43 post-birth Visit3-NB/Day 121 post-birth Visit4-NB/Day 181 post-birth	Immunogenicity
2050#*	Maternal intercurrent medical conditions which are exclusionary as per protocol up to Delivery	All	Immunogenicity
2060#*	Maternal concomitant infection related to the vaccine which may influence immune response up to Delivery	All	Immunogenicity
2070#*	Maternal concomitant infection not related to the vaccine but may influence immune response up to Delivery	All	Immunogenicity
2090.Vx	Subjects did not comply with blood sample schedule – infant: 
 For infants without cord blood, check the interval from birth to Visit 1-NB birth BS = 0 – 3 days; For PPS at Day 43 post-birth, check the interval from birth to Day 43 BS = 28 – 60 days; For PPS at Day 121 post-birth, check the interval from birth to Day 121 BS = 110 –140 days; For PPS at Day 181 post-birth, check the interval from birth to Day 181 BS = 165 – 200 days 	Visit 1-NB/Birth Visit 2-NB/Day 43 post-birth Visit3-NB/Day 121 post-birth Visit4-NB/Day 181 post-birth	Immunogenicity
2100.Vx	Serological results not available	Visit 1-NB/Birth Visit 2-NB/Day 43 post-birth Visit3-NB/Day 121 post-birth Visit4-NB/Day 181 post-birth	Immunogenicity

CONFIDENTIAL209544 (RSV MAT-004)
Statistical Analysis Plan Amendment 3

Code	Condition under which the code is used	Visit (timepoints) where the code is applicable	Applicable for analysis set/endpoint
2120.Vx*	Obvious incoherence or abnormality or error in data	Visit 1-NB/Birth Visit 2-NB/Day 43 post-birth Visit3-NB/Day 121 post-birth Visit4-NB/Day 181 post-birth	Immunogenicity
2130.Vx	Testing performed on samples not aligned with ICF	Visit 1-NB/Birth Visit 2-NB/Day 43 post-birth Visit3-NB/Day 121 post-birth Visit4-NB/Day 181 post-birth	Immunogenicity
3100	Delivery happens less than 4 weeks post-vaccination.	All	Immunogenicity

*Attribution of these elimination codes to subject need CRDL review of individual listing

#Carry forward elimination from mother to infant

Vx+ indicates subjects whose immunogenicity data will be eliminated from a specific visit onwards; Vx indicates subjects whose immunogenicity data will be eliminated from a specific visit.

BS- Blood Sample.

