9.1.2. Immunogenicity

For a given subject and given immunogenicity measurement, missing or non-evaluable measurements will not be replaced. Therefore, an analysis will exclude subjects with missing or non-evaluable measurements.

- For the within-group assessment, the descriptive analysis performed for each assay at each timepoint will exclude subjects with a missing or non-evaluable measurement.
- For the between group assessments, statistical model will be fitted based on the subjects having a result at both the baseline and the considered timepoint.

The GMT/GMC and its 95% CI will be obtained by exponentiating the mean and its 95% CI of the log-transformed titres/concentrations. All CI computed will be two-sided 95% CI.

Placental transfer is defined as the ratio of RSVPreF3 IgG-specific antibody concentrations between cord blood (or blood sample from infants collected within 3 days after birth if cord blood is not available) and maternal blood sample at delivery (or within 3 days after delivery if blood sample is not collected during delivery).

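### Table 6 has no treatment, condition or infection exclusion code for a birth sample taken from the infant on days 0–3, and the SAP does not say which per-protocol set governs the transfer ratio

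*SAP*

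**What the plan says.** Section 4.2.3.2, Table 6, lists the codes that remove an infant from the PPS. Five infant-level codes (1040, 2040, 2050, 2060 and 2070, all with the suffix Vx+) cover forbidden vaccines, forbidden medication or devices, exclusionary conditions and two kinds of infection. The medication row reads "Administration of any medication forbidden by the protocol - infant". For all five the visit column is "Visit 2-NB/Day 43 post-birth Visit3-NB/Day 121 post-birth Visit4-NB/Day 181 post-birth". The suffix removes data from a given visit onwards, after review of individual listings.

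Four other infant codes in the table (2090, 2100, 2120 and 2130) do list Visit 1-NB/Birth. Code 2090 describes the fallback birth sample: "For infants without cord blood, check the interval from birth to Visit 1-NB birth BS = 0 – 3 days".

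Maternal exposures carry over to the infant only until delivery, for example "Maternal administration of any medication forbidden by the protocol up to Delivery" and "Maternal concomitant infection related to the vaccine which may influence immune response up to Delivery". In Table 5 (section 4.2.3.1) the mother's own versions of the five codes apply at Visit 3, Visit 5/Delivery and Visit 6. For her delivery sample the instruction is "check the interval from delivery to delivery BS = (-1) – (+3) days".

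Section 9.1.2 defines placental transfer as the cord (or fallback infant) concentration over the "maternal blood sample at delivery (or within 3 days after delivery if blood sample is not collected during delivery". Section 5.2.1 bases the primary immunogenicity analysis on the PPS without saying which PPS applies to a quantity built from two subjects.

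**The concern.** Starting the infant codes at Visit 2-NB is right for cord blood, because cord blood is taken at delivery and cannot follow anything given to the infant. It is not right for the fallback sample. An infant exposed on day 1 and sampled on day 2 can lose the Day 43, 121 or 181 result under Vx+, but not the day-2 result, which is closer to the exposure.

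The retained value feeds two primary endpoints: the antibody level at birth, and the numerator of the transfer ratio, for which the geometric mean and the percentage of infants at 1 or above are tabulated. It also enters the decay model of section 5.2.2.4, where each infant's birth value sets the expected value used to flag suspected infection. The PPS thus applies its exclusion principle at the secondary timepoints and not at the primary one.

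The unspecified set for the ratio is a separate weakness. Where only one member of a pair is eligible, the programmer has to decide whether a primary endpoint keeps the pair.

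**Working it through.** The SAP gives no figure on this point, so there is none to reproduce. The check sets code coverage against sampling windows, followed by a scale calculation on assumed inputs.

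**Coverage**

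1. *Cord blood.* Taken at delivery, so infant treatment cannot precede it. No gap.
2. *Infant blood on days 0–3, no cord blood.* An exposure between birth and the draw has no matching treatment, condition or infection code at Visit 1-NB. This is a gap.
3. *Maternal sample on days +1 to +3.* An exposure after delivery but before the draw is not carried to the infant, but Table 5 applies the mother's own codes at Visit 5/Delivery. The pair drops out if the ratio needs the mother's sample in the maternal PPS, and stays in if infant PPS membership alone decides. Section 5.2.1 does not settle which.

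**Do other provisions close case 2?**

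- Code 2120 reaches Visit 1-NB but concerns incoherent or abnormal data, not treatment or infection.
- The separate evaluation of cord and infant-blood samples starts only when cord blood is missing in 20% or more of a group. It separates the samples and removes none.
- Step 1 of the decay analysis removes infants with an RSV-positive swab before sampling. It does not address treatments.
- The full analysis set (FAS) keeps the same samples.

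**Scale (assumed inputs)**

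The document history of SAP Amendment 2 gives 213 vaccinated women, so 213/3 = 71 per group at 1:1:1. This counts vaccinated women, not evaluable pairs. Let p be the share of infants without cord blood, q the share of those exposed before the draw, and f the fold effect on the sample. All three are assumptions.

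Affected infants per group = 71 × p × q. The geometric mean averages logarithms, so a share p × q of values multiplied by f shifts it by the factor f^(p × q).

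| p | q | Infants per group | f = 1.5 | f = 2 | f = 4 |
|---|---|---|---|---|---|
| 5% | 2% | 0.07 | 1.0004 | 1.0007 | 1.0014 |
| 20% | 10% | 1.42 | 1.0081 | 1.014 | 1.0281 |
| 30% | 25% | 5.33 | 1.0309 | 1.0534 | 1.1096 |

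Mid-case: 71 × 0.20 × 0.10 = 1.42 infants, and 2^0.02 = 1.014. If the exposure lowers the value, the factor is the reciprocal, 1/1.014 = 0.986. For the percentage of infants at 1 or above, one infant crossing the threshold moves the result by 1/71 = 1.4 percentage points.

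**The case against.** The strongest reply is that the gap is narrow and its content depends on the protocol. Only infants without cord blood are exposed to it. The SAP does not say which products are forbidden or which conditions are exclusionary, and it does not show that any of them could change a passively acquired titre within three days of birth. The comparative analyses are descriptive (section 6) and the decay model is exploratory, so no decision rule depends on the result. All of this stands, and it limits the point to a minor one. It does not explain why the same codes are considered worth applying six weeks later but not at birth.

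A reader might go further and infer that maternal samples drawn after treatment also remain in the transfer ratio, because carry-over stops at delivery while her sample may be up to three days later. The documents do not support that. Table 5 can remove her Visit 5 value, and nothing says that infant PPS membership alone governs the ratio. Tabulating the percentage of infants at or above 1 may hint at the infant set, but a hint is not a rule.

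Nor is the delivery limit on the carry-over codes an error in itself. Those codes remove the infant at all visits because maternal exposure could alter what crosses the placenta, and transfer ends at delivery.

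**Conclusion.** The concern holds in a limited form. For infants sampled on days 0–3 in place of cord blood, Table 6 has no treatment, condition or infection code at Visit 1-NB, so a post-exposure value stays in the infant PPS for two primary endpoints and for the exploratory decay model. On the maternal side the SAP shows only an ambiguity about which PPS defines an eligible pair.

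The true size is unknown from the SAP and probably small. Over the assumed ranges, between about 0.1 and 5.3 infants per group are affected and the geometric mean ratio changes by a factor of 1.0004 to 1.11, with about 1.01 in the mid-case. These figures rest wholly on the assumed p, q and f and on 71 infants per group. The change is worth making for consistency at the primary timepoint and because it costs little.

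**What to change.** In Table 6, add Visit 1-NB/Birth, restricted to infants whose birth sample is their own blood, to the visit column of infant codes 1040, 2040, 2050, 2060 and 2070.Vx+. In section 5.2.1 or 9.1.2, state that the transfer ratio uses only pairs in which the mother's Visit 5 sample is in the maternal PPS and the infant's birth sample is in the infant PPS. Leave the carry-over codes ending at delivery as they are, so that a maternal exposure after delivery does not remove a valid cord or infant titre.

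The cost is wording in one table, one sentence on pairing, and one programming condition. Possibly one or two pairs per group leave the PPS ratio. They remain in the FAS, which section 5.2.1 has analysed when PPS exclusions reach 5% in any group at any timepoint.
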